2.0 STUDY OBJECTIVES

2.1 Primary Objective

- To evaluate if treatment with RVX000222 as compared to placebo increases time to the first occurrence of narrowly defined MACE. Narrowly defined MACE is defined as a single composite endpoint of CV death or Non-fatal MI or Stroke.

Criteria for the evaluation of individual events will be defined in the MACE Clinical Events Committee (CEC) charter and will be based on the CDISC standardized definitions for Cardiovascular and Stroke Endpoint Events¹.

2.2 Secondary Objectives

- To evaluate if treatment with RVX000222 increases time to the first occurrence of broadly defined MACE in comparison to placebo

Broadly defined MACE is the occurrence of any of the following events:

- CV death
- Non-fatal MI
- Hospitalization for CVD events including:
 - Unstable angina AND evidence of new or presumed new progressive obstructive coronary disease, OR
 - Emergency revascularization procedures at any time and urgent revascularization procedures ≥ 30 days after the index event as defined by Hicks et al.
- Stroke
- To evaluate if treatment with RVX000222 increases time to the first occurrence of fatal or non-fatal MI, or fatal or non-fatal stroke
- To evaluate treatment group difference in all-cause mortality
- To evaluate changes in lipoprotein concentrations including apoA-I, apolipoprotein B (apoB), LDL-C, HDL-C, and triglyceride (TG) over time within and between treatment groups
- To evaluate changes in DM variables including glycated hemoglobin (HbA1c), fasting glucose, and fasting insulin over time within and between treatment groups
- To evaluate changes in ALP over time within and between treatment groups including isoforms for whole population and quartiles of ALP baseline concentration
- Assess changes in kidney function in population with baseline estimated glomerular filtration rate < 60 mL/min/1.7m²
- To evaluate the safety and tolerability of RVX000222

2.3 Exploratory Objectives

- To evaluate changes in inflammation variables including, but not limited to, high-sensitivity C-reactive protein (hsCRP), fibrinogen, and inflammatory cytokines within and between treatment groups
- To evaluate transcription (messenger RNA [mRNA]) change in whole blood from baseline to 6 weeks of treatment
- To evaluate Health Related Quality of Life (HRQOL) as measured using the EQ-5D-5L

3.0 STUDY ENDPOINTS

3.1 Primary Endpoint

The primary endpoint will be time from randomization to the first occurrence of adjudication-confirmed MACE narrowly defined as a single composite endpoint of CV Death or Non-fatal MI or Stroke.

3.2 Key Secondary Endpoints

The key secondary endpoints will be:

1. Time from randomization to the first occurrence of adjudication-confirmed MACE broadly defined between treatment groups.

Broadly defined MACE is the occurrence of any of the following events:

- CV death
 - Non-fatal MI
 - Hospitalization for CVD events which include:
 - Unstable angina AND evidence of new or presumed new progressive obstructive coronary disease, OR
 - Emergency revascularization procedures at any time and urgent revascularization procedures ≥ 30 days after the index events prior to randomization
 - Stroke
2. Time from randomization to fatal or non-fatal MI, or fatal or non-fatal stroke
 3. Time from randomization to CV Death or Non-fatal MI
 4. Time from randomization to Non-fatal MI
 5. Time from randomization to CV Death
 6. Time from randomization to Stroke
 7. All-cause mortality

3.3 Other Secondary Endpoints

- The percent change in apoA-I, apoB, LDL-C, HDL-C, and TG over time within and between treatment groups
- The change from baseline in HbA1c, fasting glucose, and fasting insulin within and between treatment groups
- Changes in ALP within and between treatment groups for all subjects and according to quartiles of ALP baseline concentration
- Changes from baseline in kidney function in subgroup population with estimated glomerular filtration rate < 60 mL/min/1.7m² within and between treatment groups

3.4 Exploratory Endpoints

- The percent change in hsCRP, fibrinogen, and inflammatory cytokines within and between treatment groups
- Transcription/mRNA change in whole blood from baseline to 6 weeks treatment within and between treatment groups
- Change in Health Related Quality of Life (HRQOL) as measured using the EQ-5D-5L

3.5 Safety Endpoints

- Safety assessments will include incidence of adverse events (AEs), serious adverse events (SAEs), vital sign measurements, clinical laboratory evaluations, Montreal Cognitive Assessment (MOCA) (for subjects \geq 70 years of age at randomization) and physical examination findings

4.0 STUDY DESIGN

This is a double-blind, placebo-controlled, 2-arm parallel-group (allocation ratio 1:1), study of RVX000222 at a daily dose of 100 mg b.i.d. (total daily dose of 200 mg) or matching placebo in combination with high intensity statin therapy administered to T2DM subjects with history of recent CAD event and HDL-C level $<$ 40 mg/dL in males or $<$ 45 mg/dL in females.

After an initial screening period of 1 to 2 weeks during which subjects will demonstrate tolerance of high intensity statin therapy, subjects will be randomized to either RVX000222 100 mg b.i.d. or matching placebo with continued statin treatment. This combination treatment period will continue until 250 narrowly defined MACE events have occurred in the study and all surviving patients have been followed for at least 24 weeks from randomization. Blinded treatment with RVX000222 or matching placebo will then be discontinued. Subjects will remain on high intensity statin therapy for 4 more weeks until the Follow-Up Visit.

The study is an event-based trial and will continue until 250 primary endpoint events have occurred. Study treatment will be terminated after the 250th adjudicated event occurs. At that time, all subjects actively treated will conduct their Last Visit on Treatment and then be discontinued from investigational drug. Subjects will then return 4 weeks after last day of treatment for the Follow-Up Visit.

A Clinical Steering Committee (CSC) will oversee the conduct of the study. A Data Safety Monitoring Board (DSMB) will oversee the safety data for this study and independent CEC will adjudicate all suspected MACE composite events in an ongoing manner. An independent team (including an independent statistician) will perform the prospective unblinded analyses described in Section 10.8 (Data Safety Monitoring Board) and will report the results to the DSMB. Each committee will develop a charter to describe their activities and responsibilities prior to initiation of the study.

5.0 STUDY POPULATION

5.1 Number of Subjects

It is estimated that enrollment of approximately 2400 male or female subjects with T2DM and high-risk CAD treated with high intensity statin therapy (atorvastatin 20-80 mg or rosuvastatin 10-40 mg) and with a low level of HDL-C of $<$ 40 mg/dL in males or $<$ 45 mg/dL in females at multiple investigational sites globally will be needed to reach the 250 MACE needed for this event-based trial.

5.2 Inclusion Criteria

Subjects who meet the following criteria may be enrolled:

1. Male and female subjects age 18 and over with documented diagnosed T2DM and a CAD event of either unstable angina or myocardial infarction, not less than 7 days and no more than 90 days prior to Visit 1. In order to have sufficient number of clinical events, the number of subjects with unstable angina will be limited to 25% of the total number of subjects.

- Unstable angina: for a qualifying unstable angina event, each of components (a), (b), and (c) must be satisfied:
 - a. Characteristic ischemic pain or discomfort in chest or associated referral areas, occurring at rest or with minimal exertion
 - b. ECG changes consistent with acute myocardial ischemia based upon at least one of the following:
 - i. new or presumed new ST elevation
 - ii. new or presumed new ST depression
 - iii. new or presumed new T-wave inversion
 - c. Objective evidence of obstructive coronary artery disease based upon at least one of the following:
 - i. new or presumed new evidence of myocardial ischemia or infarction by perfusion imaging
 - ii. new or presumed new regional wall motion abnormality
 - iii. current evidence of at least one epicardial coronary artery stenosis $\geq 70\%$ by coronary angiography
 - iv. need for coronary revascularization for the index ACS event, including percutaneous coronary intervention (PCI) with or without coronary stenting
 - Previous MI 7-90 days before screening, treated with or without a percutaneous coronary intervention (PCI). For a qualifying event of MI, **two of the following three criteria must be satisfied**:
 - a. Characteristic ischemic chest pain or pain in associated referral areas
 - b. Dynamic elevation of troponin T or I or CKMB, if troponin T or I is unavailable at the local lab (at least above the upper limit of normal for the laboratory)
 - c. Development of new Q-waves in at least two adjacent ECG leads, or development of a new dominant R wave in V1
2. Documented diagnosis of T2DM (one or more of the following criteria must be met):
 - Documented history of T2DM
 - History of taking diabetes medication
 - HbA1c $\geq 6.5\%$ at Visit 1
 3. For males HDL-C of <40 mg/dL (1.04 mmol/L) and for females HDL-C of <45 mg/dL (1.17 mmol/L) at Visit 1.
 4. In the opinion of the Investigator, subjects currently not on high intensity statin therapy will be able to start rosuvastatin according to the protocol at Visit 1.
 5. In the opinion of the Investigator, subjects currently on statin therapy other than atorvastatin or rosuvastatin can be switched to rosuvastatin according to the protocol at Visit 1. High intensity statin therapy doses should remain unchanged during the study period if at all possible.
 6. Female subjects must meet one of the following:
 - If of childbearing potential, female subjects must have a negative urine pregnancy test and be willing and able to use medically acceptable non-hormonal method of birth control (non-hormonal intrauterine device, condom, or diaphragm) or remain abstinent from Screening until Follow-up Visit.
 - Be of non-child-bearing potential: post-surgical sterilization or post-menopausal.
 7. Have given signed informed consent to participate in this study.

5.3 Exclusion Criteria

Subjects who meet any of the following criteria will not be enrolled:

1. Heart disease which, in the opinion of the investigator, will within 90 days of Visit 1 likely require coronary bypass, PCI, cardiac transplantation, surgical repair and/or replacement.
2. Previous or current diagnosis of severe heart failure (New York Heart Association Class IV) or a documented left ventricular ejection fraction (LVEF) of <25% as determined by contrast left ventriculography, radionuclide ventriculography or echocardiography. The absence of an LVEF measurement in a subject without a previous or current diagnosis of heart failure does not prohibit entry into the study.
3. Subjects with evidence of cardiac electrophysiologic instability including a history of uncontrolled ventricular arrhythmias, uncontrolled atrial fibrillation/flutter or uncontrolled supraventricular tachycardias with a ventricular response heart rate of >100 beats per minute at rest within 4 weeks prior to Visit 1.
4. Coronary artery bypass grafting (CABG) within 90 days prior to Visit 1.
5. Evidence of severe renal impairment as determined by any one of the following:
 - an estimated Glomerular Filtration Rate less than 30 mL/min/1.7m² at Visit 1
 - a current need for dialysis
6. Uncontrolled hypertension defined as 2 consecutive measurements of sitting blood pressure of systolic >180 mm Hg or diastolic >100 mm Hg at Visit 1.
7. Subjects at risk of immunosuppression, including current or recent (within 12 months prior to Visit 1) treatment with immunosuppressants (e.g., cyclosporine).
8. Use of fibrates at any dose or niacin/nicotinic acid 250 mg or more within 30 days prior to Visit 1.
9. A known allergy or sensitivity to any ingredient in the investigational medicinal product.
10. History of intolerance to atorvastatin or rosuvastatin. This exclusion criterion applies to subjects with a history of intolerance to the statin to which they would be assigned at screening.
11. Triglycerides >400 mg/dL (4.52 mmol/L) at Visit 1.
12. Any medical or surgical condition which might significantly alter the absorption, distribution, metabolism or excretion of medication including, but not limited to, any of the following: Untreated or incompletely treated thyroid dysfunction, cholecystitis, Crohn's disease, ulcerative colitis, or any gastric bypass alteration.
13. Evidence of cirrhosis from liver imaging or biopsy, a history of hepatic encephalopathy, esophageal or gastric varices, active hepatitis, or prior porta-caval shunt procedure, or a Child-Pugh score of at least 5 points (Appendix A).
 - Any one of the following liver enzymes that is >1.5xULN by central lab at Visit 1
 - a. ALT
 - b. AST
14. A total bilirubin that is >ULN by central lab at Visit 1.
15. History of malignancy of any organ system, treated or untreated, within the past 2 years whether or not there is evidence of local recurrence or metastases, with the exception of localized basal cell carcinoma of the skin.
16. History or evidence of drug or alcohol abuse within 12 months of Visit 1, in the opinion of the investigator.
17. Female subjects who are pregnant.
18. Any condition which, in the opinion of the investigator, may place the subject at higher risk from his/her participation in the study, or is likely to prevent the subject from complying with the

requirements of the study or completing the study, including subjects at risk of immunosuppression.

19. Use of other investigational drugs and devices within 30 days or 5 half-lives of Visit 1, whichever is longer.
20. History of noncompliance to medical regimens or unwillingness to comply with the study protocol.
21. Any condition that, in the opinion of the investigator, would confound the evaluation and interpretation of efficacy and/or safety data.
22. Persons directly involved in the execution of this protocol.

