7.1.4.6 Liver Safety Panel

ALT (SGPT), AST (SGOT), gammaglutamyl transferase (GGT), ALP, and bilirubin (direct and total) will be measured at each visit as indicated on the Schedule of Events (

	Screen																			
Fasting Lipid profile												x	11	12	13	14	15	16	17	18
Hematology, HbA1c	x											x			x		x		x	
Urine Urinalysis	x											x			x		x		x	
Hepatitis Serology	- 2 to -1	0	2	4	6	8	10	12	16	20	24	28	40	52	64	76	88	100		
Liver Safety Panel	x	x	x	x	x	x	x	x	x	x	x	x	x	x	x	x	x	x	x	
Biomarker Laboratory Tests			±3	±3	±3	±3	±3	±3	±3	±3	±3	±3	±3	±7	±7	±7	±7	±7	±7	
Fasting insulin	x	x											x			x		x		
Inflammation Panel		x														x				
Serum/Plasma Archive	x	x														x				
Pharmacogenomics	x	x			x															
Medical History/Demographics	x	x																		
MOCA	x	x																		
EKG	x	x																		
Vital Signs	x	x																		
Adverse Events	x	x	x	x	x	x	x	x	x	x	x	x	x	x	x	x	x	x		
Physical Exam	x	x	x	x	x	x	x	x	x	x	x	x	x	x	x	x	x	x		
Prior / Con. Medication																				
Central Laboratory																				
Drug Dispense/Account.																				

Table 1).

As defined in Section 6.10.1, subjects who have an ALT increase of $\geq 3xULN$ will be monitored by liver safety panels and have archival serum samples drawn every 3-4 days until ALT values return to $<1.5xULN$ and subjects who have an ALT increase of $>5xULN$ or who have a serum bilirubin increase of $>2xULN$ will be monitored by extended liver safety panels and have archival serum samples drawn every 3-4 days until ALT values return to $<1.5xULN$ or serum bilirubin values return to within normal range.

The Extended Liver Panel includes ALT (SGPT), AST (SGOT), GGT, ALP, bilirubin (direct and total), as well as osteopontin and PT INR

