9.3 Analysis Sets

Full Analysis Set (FAS): The FAS will include all randomized subjects who receive any amount of study therapy and have at least one measurement of the assessment of interest. All efficacy analyses will be conducted for the FAS set. Subjects will be analyzed based on randomized treatment group.

Per-protocol Set (PPS): The PPS will consist of all FAS subjects who fulfill all inclusion/exclusion criteria, and have no other major protocol violations. The major protocol violation criteria will be finalized by the Clinical Science and Biostatistics teams as part of the treatment-blinded data review prior to the interim and final database locks. Likewise, whenever possible, subjects belonging to the PPS will be determined prior to the interim and final database locks.

Safety Set (SS): The SS will include all subjects who took at least one dose of double-blind study therapy. In safety summaries, subjects will be analyzed according to the actual treatment received. All safety analyses will use the SS.

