13.0 APPENDICES

APPENDIX A: CHILD-PUGH CLASSIFICATION^{9,10}

Child- Turcotte-Pugh (CTP) classification of the severity of cirrhosis

	Points*		
	1	2	3
Encephalopathy	None	Grade 1-2 (or precipitant-induced)	Grade 3-4 (or chronic)
Ascites	None	Mild/Moderate (diuretic-responsive)	Severe (diuretic-refractory)
Bilirubin (mg/dL)	<2	2-3	>3
Albumin (g/dL)	>3.5	2.8-3.5	<2.8
PT (sec prolonged) or INR	<4 <1.7	4-6 1.7-2.3	>6 >2.3

CTP score is obtained by adding the score for each parameter

CTP class: A = 5-6 points
 B = 7-9 points
 C = 10-15 points

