4.4.2. Per-protocol Set (PPS)

The PPS will consist of all FAS subjects who fulfill all inclusion/exclusion criteria, and have no major protocol violations. The major protocol violation criteria will be finalized by the Clinical Science and Biostatistics teams as part of the masked data reviews prior to the interim and final database locks. Likewise, whenever possible, subjects belonging to the PPS will be determined prior to the interim and final database locks. Subjects will be analyzed based on the treatments received most often. The list of major protocol violations is provided in [section 5.2](#) of this statistical analysis plan.

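### Exclusion 13 sets its Child-Pugh limit at 5 points, the lowest score Appendix A can give, without saying to whom the score applies, so eligibility and formal per-protocol membership cannot be settled as written

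*Protocol*

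**What the plan says.** Exclusion 13 appears in Protocol 5.3 and again in the synopsis. It lists imaging or biopsy evidence of cirrhosis and several related liver conditions, and closes that list with "or a Child-Pugh score of at least 5 points (Appendix A". Section 5.3 opens with the rule "Subjects who meet any of the following criteria will not be enrolled".

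Appendix A presents the scale as a "classification of the severity of cirrhosis". It has five rows (encephalopathy, ascites, bilirubin, albumin, PT or INR), each worth 1, 2 or 3 points. It states that "CTP score is obtained by adding the score for each parameter", and its lowest band is "CTP class: A = 5-6 points". The top band, class C, ends at 15.

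Eligibility also defines the per-protocol set. Protocol 9.3 reads "The PPS will consist of all FAS subjects who fulfill all inclusion/exclusion criteria, and have no other major protocol violations". SAP 4.4.2 keeps the same first condition, "The PPS will consist of all FAS subjects who fulfill all inclusion/exclusion criteria", and adds the absence of major violations. SAP 5.2 names four expected major violations, and Child-Pugh is not among them.

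The Visit 1 procedures (Protocol 7.2.1) include chemistry, which gives albumin, and the liver safety panel, which gives bilirubin. They list neither PT/INR nor Child-Pugh scoring. PT/INR belongs to a different panel (Protocol 7.1.4.6): "The Extended Liver Panel includes ALT (SGPT), AST (SGOT), GGT, ALP, bilirubin (direct and total), as well as osteopontin and PT INR". That panel is used after ALT rises above 5×ULN or bilirubin above 2×ULN.

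**The concern.** A limit placed at the bottom of a scale cannot separate one subject from another. Exclusion 13 joins the score to the other liver conditions with an or, and none of its words restrict the score to people with liver disease. Taken at face value, a candidate with five normal parameters is excluded.

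Two things depend on how the clause is read. The first is eligibility: Protocol 7.2.2 allows randomization only when all criteria are satisfied, so literally every randomization would breach criterion 13. The second is the PPS, which supports the primary analysis (SAP 8.2) and the key secondary analyses (SAP 8.3). Its definition requires every criterion to be met. Filling the set therefore rests on a reading of exclusion 13 that neither document records.

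**Working it through.** **Inputs.** Five parameters, each scored 1 to 3 and summed (Appendix A); exclusion at 5 or more (Protocol 5.3, item 13, and synopsis); PPS conditions (Protocol 9.3, SAP 4.4.2); Visit 1 tests (Protocol 7.2.1).

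1. **Reproduce the appendix's own range.** Minimum = 5 × 1 = 5 and maximum = 5 × 3 = 15. This matches the bands, where class A starts at 5 and class C ends at 15, so the table has been read correctly.

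2. **Apply the limit to every possible score.** There are 3^5 = 243 combinations. Those totalling 5 or more: 243. Those below 5: 0.

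3. **Restrict to candidates who pass the neighbouring criteria.** Exclusion 13 bars a history of encephalopathy and exclusion 14 bars total bilirubin above the ULN. Fix both parameters at 1 point; for bilirubin this assumes a central-laboratory ULN below 2 mg/dL, which the documents do not state. The other three parameters give 3^3 = 27 combinations, with a minimum total of 1 + 1 + 3 = 5. Those totalling 5 or more: 27 of 27.

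4. **Allow for the missing PT/INR.** The other four parameters total at least 4, and any PT/INR result adds at least 1, so the total is at least 5. The absent test does not change the literal result. It bears only on whether scoring of all candidates was intended.

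5. **Compare the two readings.**
   - *Score applies to everyone:* all candidates meet the exclusion. Literally, 0 of about 2400 subjects fulfil all criteria, so the PPS has no members.
   - *Score applies only to people with cirrhosis:* everyone to whom the scale applies still scores at least 5. The clause then means cirrhosis of any class. It adds at most cirrhosis identified by means other than imaging or biopsy, because the first part of the criterion already covers those two.

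   On neither reading does the number 5 distinguish between subjects.

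6. **Trace what depends on it.** The full analysis set (Protocol 9.3, SAP 4.4.1) requires randomization, some study therapy and at least one measurement of the assessment of interest. It does not test eligibility. The primary analysis uses that set, and the power rests on 250 events and a hazard ratio of 0.7. None of these depends on exclusion 13. Only PPS membership does.

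**The case against.** The strongest reply is that the scope is supplied by the appendix to which the criterion points. Appendix A describes a scale for grading cirrhosis, 5 is where its mildest class begins, and the rest of the criterion lists cirrhosis and its complications. A score of 5 or more would then be shorthand for cirrhosis of any class. The lack of PT/INR and of any scoring step at Visit 1 supports this, since a protocol that meant to score every candidate would have provided for it. The reading need not be wholly redundant either, because cirrhosis can be diagnosed without imaging or biopsy.

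Much of this stands. It is a plausible account of the intent, and it makes literal application by sites unlikely. It does not settle the text: the restriction is absent from exclusion 13, which presents the score as a separate alternative, and the limit remains idle under the narrower reading.

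A reader might also infer that liver screening will differ between sites, which would matter for a drug whose dose-limiting toxicity is raised transaminases. The documents do not show this. The ALT and AST limits and the bilirubin limit are objective, use the central laboratory at Visit 1, and work independently of the Child-Pugh clause.

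On the PPS, it can be said that the violation criteria are finalised in blinded review and that the SAP 5.2 list omits Child-Pugh. That makes an empty set unlikely in practice. It does not remove the wording problem, because meeting all criteria is a separate condition from having no major violation.

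**Conclusion.** The point holds as a defect of wording. The 5-point limit equals the floor of the scale. Literally it is met by 243 of 243 score combinations; on the narrower reading it is met by everyone with cirrhosis and adds little to the criterion. This rests only on Appendix A's scoring rule and the text of exclusion 13.

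A reader might go further and expect the trial to enrol nobody, or the PPS to contain 0 of about 2400 subjects. Those figures describe the literal text and do not predict conduct; the Visit 1 procedures suggest that universal scoring was never intended. Nor is the primary result at risk: the full-analysis-set comparison, the 250 events and the power are untouched. What is exposed is the eligibility wording and the formal membership of a supportive analysis set. It should be corrected because it is a stated rule that fails when followed, and the correction is cheap.

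**What to change.** Reconcile exclusion 13, in both Protocol 5.3 and the synopsis, with Appendix A and the Visit 1 tests. The revised text should state to whom the Child-Pugh clause applies. If a score is to be determined at screening, it should also say where each of the five components, including PT/INR, is obtained. The clinical content of the criterion is for the sponsor to decide.

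For the PPS, record in SAP 4.4.2 or 5.2, before the database locks, how the clause is applied when checking that all criteria are met. Membership then follows from the written plan and not from an unrecorded reading.

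The cost is about one sentence in the next protocol amendment, repeated in the synopsis, and one line in the SAP. No new procedure is needed unless the sponsor decides that every candidate should be scored, in which case PT/INR would have to be added at Visit 1.
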